5.3.1. Analyses for Time to Event Data

Time to event endpoints in this study include progression-free survival (PFS), duration of response (DOR), duration of stable disease (DoSD), time to response (TTR), time to progression (TTP), and overall survival (OS). When appropriate and data permits, the immune-response version of these endpoints based on irRECIST will also be explored. The specific definitions of these endpoints are provided in [Section 3](#). These endpoints will be summarized using the Kaplan-Meier method² and displayed graphically when appropriate. Median event times and 2-sided 95% confidence intervals for each time-to-event endpoint (Brookmeyer and Crowley, 1982)³ will be provided.

5.3.2. Analyses for Binary Data

Binary endpoints in this study include ORR, complete response (CR), partial response (PR) based on RECIST 1.1. When appropriate and data permits, the immune-response version of these endpoints based on irRECIST will also be explored. If deemed necessary disease control rate (i.e. DCR, which is defined as the proportion of patients that achieved CR, or PR, or stable disease) may also be calculated for Part 2. Descriptive statistics along with the corresponding 2-sided 95% confidence intervals using an exact method will be provided for these endpoints.

5.3.3. Analyses for Continuous Data

Descriptive statistics, such as the mean, standard deviation, coefficient of variation, median, minimum, and maximum values, will be provided for continuous endpoints.

5.4. Methods to Manage Missing Data

5.4.1. Missing Dates

In compliance with Pfizer standards, if the day of the month is missing for any date used in a calculation, the 1st of the month will be used to replace the missing date unless the calculation results in a negative time duration (eg, date of onset cannot be prior to day one date). In this case, the date resulting in 0 time duration will be used. Pfizer standards are also used if both month and day are missing (Jan 1 unless negative time duration). This excludes the pharmacokinetic, ECG, and pharmacodynamic analyses, which will only use the actual date collected or if date not available deem the data missing.

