6.5. Survival Follow-up

To collect OS data, patients will be contacted by telephone every 8 weeks (± 7 days) post 120 day follow up visit, until end of the trial (2 years after last patient first dose). If the patient is seen in the clinic during the window of time that a scheduled telephone call is to be made to collect survival data, then the clinic visit may replace the survival telephone call. After the completion of the EOT visit subsequent anti-cancer therapy will be documented and recorded for patients who discontinue investigational products and continue in 120 day safety follow-up, and subsequently during survival follow-up.

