All reasonable efforts must be made to locate patients to determine and report their ongoing status. This includes follow-up with persons authorized by the patient as noted above. Lost to follow-up is defined by the inability to reach the patient after a minimum of 2 documented phone calls, faxes, or e-mails as well as lack of response by the patient to 1 registered mail letter. All attempts should be documented in the patient's medical records. If it is determined that the patient has died, the site will use permissible local methods to obtain the date and cause of death. If the investigator's use of a third-party representative to assist in the follow-up portion of the study has been included in the patient's informed consent, then the investigator may use a sponsor-retained third-party representative to assist site staff with obtaining the patient's contact information or other public vital status data necessary to complete the follow-up portion of the study. The site staff and representative will consult publicly available sources, such as public health registries and databases, in order to obtain updated contact information. If, after all attempts, the patient remains lost to follow-up, then the last-known-alive date as determined by the investigator should be reported and documented in the patient's medical records.

If the patient refuses further visits, the patient should continue to be followed for survival unless the patient withdraws consent for disclosure of future information or for further contact. In this case, no further study specific evaluations should be performed, and no additional data should be collected. The sponsor may retain and continue to use any data collected before such withdrawal of consent.

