- Time to event endpoints by PF-06801591 administered by SC based on RECIST and irRECIST, including time to response (TTR) and time to progression (TTP) as well as PFS (and irPFS as appropriate), DOSD (and irDOSD as appropriate), and DOR (and irDOR as appropriate). Time to response is defined as the time from the study treatment date to the first documentation of PR or CR. Time to progression is the time from start date to date of first documentation of objective progression.
- *Median time to death, proportion of patients alive at 6 months, 1 year, and 2 years.* Time to death (i.e. overall survival) is the time from treatment start date to date of death due to any cause.
- Trough PF-06801591 concentrations for selected cycles.
- Incidence of ADA and NAb against PF-06801591 administered by SC.

CCI

Detailed descriptions of Endpoints are provided in [Appendice 9.1](#), [9.4](#), and [9.5](#).

CCI

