5.4.2. Efficacy Analysis

For the time-to-event endpoints, the missing data handling method will be censoring. Censoring rules for time-to-event endpoints are detailed in [Appendix 9.2](#).

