9.2. Time to Event Data Analysis Censoring Rules

Table 9.2.1: Progression Free Survival and Duration of Response

Situation	Date of Progression/Censoring¹	Outcome
Inadequate baseline assessment	First dosing date in Cycle 1	Censored
No on-study assessments	First dosing date in Cycle 1	Censored
Alive over the course of the study and no progression	Date of last objective tumor assessment	Censored
Progression or death documented on or between scheduled tumor assessments	Date of first objective tumor assessment showing objective progression or death date	Progressed/Death (Event)
Treatment discontinuation for undocumented progression	Date of last objective tumor assessment	Censored
Treatment discontinuation due to toxicity or other reason	Date of last objective tumor assessment	Censored
Progression/Death prior to second planned tumor	Date of death	Progressed/Death (Event)
Death or progression after 2 or more missed tumor assessments	Date of last objective tumor assessment prior to the event	Censored

1. For date of censorship, if a tumor assessment takes place over a number of days (eg, superficial lesions one day, scans another), the last date is used as the assessment date.
2. The first two reasons (Inadequate baseline assessment; No on-study assessments) are not applicable for Duration of Response, as that endpoint is only for the subset of responders.

Table 9.2.2: Time to Progression

Situation	Date of Progression/Censoring¹	Outcome
Inadequate baseline assessment	First dosing date in Cycle 1	Censored
No on-study assessments	First dosing date in Cycle 1	Censored
Alive over the course of the study and no progression	Date of last objective tumor assessment	Censored
Progression Documented on or between scheduled tumor assessments	Date of first objective tumor assessment showing objective progression	Progressed (Event)
Treatment discontinuation for undocumented progression	Date of last objective tumor assessment	Censored

Situation	Date of Progression/Censoring¹	Outcome
Treatment discontinuation due to toxicity or other reason	Date of last objective tumor assessment	Censored
New anticancer treatment prior to documented progression	Date of last objective tumor assessment prior to new anticancer treatment	Censored
Death prior to first planned tumor assessment	Start date (C1D1)	Censored
Death without objective progression	Date of last objective tumor assessment prior to death	Censored

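### SAP 5.4.1, as worded, can date a death before a contact at which the patient was known to be alive; the effect on OS is probably small and the repair is cheap

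*SAP*

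**What the plan says.** SAP 5.4.1 gives one default for incomplete dates and applies it to every date that enters a calculation. With the day missing, "the 1st of the month will be used to replace the missing date unless the calculation results in a negative time duration"; with day and month missing, 1 January is used under the same limit. The section attributes this to a sponsor standard that is not among the documents. It exempts PK, ECG and pharmacodynamic analyses and nothing else. Its one example of the limit is an onset date; death is not named.

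Death dates do enter a calculation. SAP 3.2 states: "Time to death (i.e. overall survival) is the time from treatment start date to date of death due to any cause". Median OS and the proportions alive at 6 months, 1 year and 2 years are Part 2 secondary endpoints.

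Two other places touch missing data for OS. SAP 5.4.2 says: "For the time-to-event endpoints, the missing data handling method will be censoring". It points to Appendix 9.2, whose tables cover PFS/DOR and TTP but not OS. The OS row of the overview table in SAP 6.3.1 lists censoring at the last visit. Neither mentions a death that is known to have happened on an incompletely known date.

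In the protocol, section 6.5 says that after the 120-day visit "patients will be contacted by telephone every 8 weeks". Under section 6.6, if a patient is found to have died, "the site will use permissible local methods to obtain the date and cause of death"; if the patient stays lost to follow-up, "then the last-known-alive date as determined by the investigator should be reported". No analysis rule uses that last-known-alive date.

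**The concern.** For OS, the non-negative-duration limit means only that death cannot precede treatment start. A patient seen alive on 14 May whose death is recorded only as May is dated dead on 1 May, 13 days before that contact. The study's own records contradict such a date.

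The imputed date is always the earliest in the recorded month or year, or treatment start if that is later. Where the rule governs, the OS error therefore never lengthens survival. Two programmers could also treat the same patient differently: one imputes the death under 5.4.1, the other censors under 5.4.2 or the OS row of 6.3.1.

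**Working it through.** The plan states no figure on this point, so there is none to reproduce. The rule was applied literally and compared with a floor.

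**1. Formulas.**
- SAP date = max(1st of month or 1 January, treatment start).
- Floored date = max(SAP date, last alive contact + 1 day).

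**2. Worked dates** (treatment start 1 October 2018).

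| Last alive contact | True death (OS) | Missing | SAP date (OS) | Against the contact | Floored date (OS) |
|---|---|---|---|---|---|
| 20 Mar 2019 | 28 Mar 2019 (178 d) | day | 1 Mar 2019 (151 d) | 19 d before | 21 Mar 2019 (171 d) |
| 20 Mar 2019 | 28 Mar 2019 (178 d) | month and day | 1 Jan 2019 (92 d) | 78 d before | 21 Mar 2019 (171 d) |
| 20 Oct 2019 | 28 Nov 2019 (423 d) | day | 1 Nov 2019 (396 d) | 12 d after | 1 Nov 2019 (396 d) |
| 20 Oct 2019 | 28 Nov 2019 (423 d) | month and day | 1 Jan 2019 (92 d) | 292 d before | 21 Oct 2019 (385 d) |

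**3. Size per affected death** (simulation). From the documents: 56-day contacts (Protocol 6.5) and cut-off 2 years after last patient first dose (Protocol 13). Assumed: exponential OS with median 12 or 18 months, and uniform accrual over 12 months from 1 January.

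| Missing | Mean shortening, SAP rule | With floor | Share left (lower end) | SAP date strictly before last contact* |
|---|---|---|---|---|
| Day | 14.4–14.5 d | 11.8 d | 11.8/14.4 = 82% | 26% |
| Month and day | 143–152 d | 25.6 d | 25.6/143 = 18% | 93% |

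*Among deaths that follow at least one 8-weekly contact.

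A second simulation used medians of 10.4 and 12.2 months (from the anti-PD-1 trials in Protocol 1.2.5) and deaths within 2 years of each patient's start. With all deaths in the denominator, including those before the first contact, the shares are about 22% and 79–80%. Across contact intervals of 28 to 63 days they are about 20–46% and 76–89%.

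**4. Size for the group.** N=70 (NSCLC target, Protocol 9.3), true median OS 12 months, 1,500 simulated trials per scenario. All rates of partial dates are assumed. On complete dates the mean Kaplan-Meier median is 11.85 months.

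| Deaths with a partial date | Median OS, SAP rule | Shift |
|---|---|---|
| 5% day | 11.83 | 0.02 |
| 20% day | 11.76 | 0.09 |
| 2% month and day | 11.76 | 0.09 |
| 10% day plus 5% month and day | 11.57 (floor 11.78) | 0.28 |

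In the last row, 1-year OS moves from 49.9% to 49.0% (floor 49.6%). The sampling SDs are 2.1 months and 6.1 points, so the shifts are 0.28/2.1 = 0.13 and 0.9/6.1 = 0.15 SD. With a true median of 18 months and the same rates, the median moves from 17.8 to 17.5 months (floor 17.7).

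**5. PFS and DOR.** Here the error can go either way, because Table 9.2.1 censors "Death or progression after 2 or more missed tumor assessments" at the last assessment before the event. Example: last scan 21 January, scans missed 18 March and 13 May, death 20 May recorded only as May. The true date gives censoring at 21 January; the imputed date gives an event on 1 May. Among simulated deaths 1–30 days after a second missed 8-weekly scan with the day missing, 46% change from censored to event, dated on average 102 days after the censoring date. With the floor it is 37%, so 37/46 = 80% of the changes remain.

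**The case against.** **The OS row of SAP 6.3.1 may be the specific rule that displaces 5.4.1.** Applied to known deaths it would censor observed events, which is a strained reading. It fits patients without a recorded death better. But the SAP does not say so, and any repair must reconcile 5.4.1, 5.4.2 and that row together.

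**The sponsor standard may already treat death dates separately.** This cannot be excluded. The point concerns the SAP text as it stands.

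**The effect is immaterial.** Largely right. OS is descriptive, with no hypothesis test. The 8-weekly calls, the sites' search for the date of death, and the reporting of deaths within 150 days of last dose as SAEs (Protocol 8.2) all make partial dates less likely, missing months above all. A reader might infer that reported OS will be materially biased downwards; the documents give no rate of partial dates, and the assumed rates do not show it.

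**The floor does little when only the day is missing, and the PFS/DOR example is unlikely.** Both stand. About 80% of the day-only error and of the PFS/DOR changes remain. Scans become 12-weekly after end of treatment, and deaths soon after dosing fall under SAE reporting.

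A reader might also infer that TTP needs a matching change, because an imputed new-therapy date could precede a progression and trigger the Table 9.2.2 row "New anticancer treatment prior to documented progression". The documents support this poorly. Absent rapid clinical deterioration, progression is confirmed by a scan at least 4 weeks later (Protocol 7.4). With a 28-day gap between progression and new therapy, the order reverses for 18 of 365 progression dates (5%); at 35 days, for none. Forcing progression first would only swap one directional assumption for another.

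**Conclusion.** The point holds as a minor defect of the SAP text. The rule can produce death dates that contact records contradict, its OS error runs in one direction, and the SAP does not say which of its provisions governs a known death with a partial date.

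The benefit of a repair is to exclude impossible dates and to limit the large errors when month and day are both missing. It is not a correction of a sizeable bias in median OS. The existence of the problem follows from the wording and the worked dates alone. Its size rests on the assumed rates, exponential survival, the assumed accrual and regular 56-day contacts.

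**What to change.** In SAP 5.4.1, set a partial death date to the later of the imputed date and the day after the last documented contact at which the patient was alive (clinic, telephone or other source), but not beyond the end of the recorded month or year. State that a known death with a partial date is an event under this rule, and that the missing-data wording in SAP 5.4.2 and in the OS row of SAP 6.3.1 applies only to patients without a recorded death. Use the same floored death date for PFS and DOR. If the sponsor standard already contains such a floor, quote it in the SAP.

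The cost is two or three sentences and one derived date. The contacts are already scheduled (clinic visits, 90- and 120-day calls, 8-weekly survival calls). The last-alive date has to be derived from them, because Protocol 6.6 requires it to be reported only for patients lost to follow-up. Trial conduct does not change.

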5.4.2. Efficacy Analysis

For the time-to-event endpoints, the missing data handling method will be censoring. Censoring rules for time-to-event endpoints are detailed in [Appendix 9.2](#).

5.4.3. Pharmacokinetics

Concentrations below the limit of quantification

In all data presentations (except listings), concentrations below the limit of quantification (BLQ) will be set to zero. (In listings BLQ values will be reported as “<LLQ”, where LLQ (i.e. lower limit of quantification) will be replaced with the value for the LLQ).

Deviations, missing concentrations and anomalous values

Patients who experience events that may affect their PK (eg, incomplete dosing) may be excluded from the PK analysis.

In summary tables and plots of median profiles, statistics will be calculated with concentrations set to missing if one of the following cases is true:

1. A concentration has been reported as ND (ie, not done) or NS (ie, no sample),
2. A deviation in sampling time is of sufficient concern or a concentration has been flagged anomalous by the pharmacokineticist.

Note that summary statistics will not be presented at a particular time point if more than 50% of the data are missing.

An anomalous concentration value is one that, after verification of bioanalytical validity, is grossly inconsistent with other concentration data from the same individual or from other subjects. For example, a BLQ concentration that is between quantifiable values from the same dose is considered as anomalous. Anomalous concentration values may be excluded from PK analysis at the discretion of the PK analyst.

Pharmacokinetic parameters

Actual PK sampling times will be used in the derivation of PK parameters. If a PK parameter cannot be derived from a subject’s concentration data, the parameter will be coded as NC (ie, not calculated). (Note that NC values will not be generated beyond the day that a subject discontinues).

In summary tables, statistics will not be presented for a particular treatment group if more than 50% of the data are NC. For statistical analyses, PK parameters coded as NC will also be set to missing.

If an individual subject has a known biased estimate of a PK parameter, this will be footnoted in summary tables and will not be included in the calculation of summary statistics or statistical analyses.

CCI

5.5. Statistical Considerations of COVID-19 Impacted Data

In March 2020, prior to the database release for this study, the World Health Organization (WHO) announced a global pandemic of the virus SARS-CoV-2 and the resulting disease COVID-19. During the conduct of this trial, if any participant's data is impacted by this pandemic, the following considerations will be given in the data analyses:

- a. Death caused by COVID-19 is still considered as an "event" in the analysis of PFS (Parts 1 and 2) and OS (Part 2). If deemed necessary, a sensitivity analysis may be performed where COVID-19 driven death is censored at the death date.
- b. If a scheduled tumor radiographic scan is *delayed* out of the Schedule of Activity allowable window, or is *missing* (i.e. participant skipped a scheduled tumor radiographic scan) due to any reasons related to the pandemic, this delay or missingness does not alter the censoring rules for PFS or TTP. A censoring reason of "COVID-19" may be added to the PFS or TTP summary if the specific reason of tumor scan delay or missing can be attributed to COVID-19. If deemed necessary, a sensitivity analysis may be performed where participants would be censored on the date of COVID-19 diagnosis.

In the confirmed ORR analysis, as described in Section 6, if a response can't be confirmed by a subsequent tumor scan because of the pandemic (i.e. the subsequent tumor scan wasn't performed), then the initial response will be considered as unconfirmed. This is a conservative approach. No sensitivity analysis will be performed.

- c. Any COVID-19 related symptoms are to be captured as adverse events in the case report form. Those adverse events will be summarized in the same manner as other adverse events. If a label of COVID-19 can be identified in the investigator provided adverse event term, then a separate AE listing may be provided for just the COVID-19 related events.
- d. If identifiable, the COVID-19 related data points, including missing data where the reason of missing is identified as COVID-19 related (site closure hence data could not be captured; participants skipped a visit because of concern over the pandemic), protocol deviations driven by COVID-19, safety events caused by COVID-19 may be separately listed.

6. ANALYSES AND SUMMARIES

For efficacy related endpoints in this study, as both RECIST 1.1 and irRECIST will be used for tumor assessments, and there are different requirements in these criteria in terms of confirming tumor response or progression, the following analysis plan will be implemented:

Endpoint	Part 1		Part 2	
	RECIST 1.1	irRECIST	RECIST 1.1	irRECIST
ORR (or irORR)	Unconfirmed	Both	Both	Both
PFS (or irPFS)	Unconfirmed	Both	Unconfirmed*	Both
DOR (or irDOR)	Unconfirmed	Both	Both	Both
DOSD (or irDOSD)	Unconfirmed	Both	Both	Both
TTP	Unconfirmed	Both	Unconfirmed*	Both
TTR	Unconfirmed	Both	Both	Both

Note: “Both” in the above table represents both unconfirmed and confirmed tumor assessments.

*: Confirmation for progressed disease is not applicable in RECIST 1.1

In the “unconfirmed” analyses (i.e. tumor response or progression without confirmation required), all tumor assessments data will be included for analyses. Specifically, regardless if a patient’s tumor response or progression is subsequently confirmed or not, the patient data will all be included in the “unconfirmed” analyses. This is a more comprehensive analysis where tumor confirmation is not required and not taken into account. For example in the ORR analysis, if a patient achieved CR or PR, regardless it is subsequently confirmed or not, the patient will be included in the numerator.

In the “confirmed” analyses (i.e. tumor response or progression with confirmation required), only those tumor assessments data that’s subsequently confirmed by a consecutive tumor scan will be considered as a “success” or “event” and be included for analyses as appropriate. For example, in the ORR analysis, a patient will only be counted in the numerator (the “success”) if the tumor response (CR or PR) is subsequently confirmed. If a patient’s tumor response is not subsequently confirmed, the patient will still be included in the denominator (the population set) but will not be included in the numerator (the “success”). In the PFS analysis, only a PD that’s subsequently confirmed will be considered as an “event”.

